1.0 Objectives

In this multistep study, we will build on our prior efforts¹ to develop consensus on surveillance mammography and follow-up for breast cancer survivors who are age ≥ 75 by further developing expert-panel recommendations, examining clinician and patient attitudes towards these recommendations, and testing a strategy for communication of expert recommendations on mammography cessation through direct engagement of specialists, primary care clinicians (PCs), and patients. Specifically, we will work to reduce overscreening of older patients through the following aims:

- 1.1 Develop a communication tool that summarizes recommendations for clinicians and patients for surveillance mammography and follow-up care for breast cancer survivors age ≥ 75 . This will build off the work of a multidisciplinary expert panel which will come together for a meeting to develop draft recommendations (OHRS exempt protocol #18-526).
 - Interview up to 30 patients through telephone-based patient interviews and focus groups and interview oncologists and primary care providers (PCs) through 4-6 focus groups to learn their perceptions and thoughts about when to stop surveillance mammography, how to thoughtfully incorporate life expectancy into decision-making, how to communicate the benefits/risks of surveillance mammography, obtain feedback on the communication tool, and to explore optimal strategies for integrated and unified care between disciplines
 - Perform cognitive testing of the communication tool in up to 10 Dana-Farber breast cancer patients and further refine it for Aim 1.2
- 1.2 Test the surveillance mammography communication tool with older breast cancer survivors and their oncology clinicians
 - In a pre-post intervention study, examine the effect of the communication tool among 45 breast cancer survivors age ≥ 75 years (with low risk of in-breast recurrences) seen by oncologists on women's intentions for and knowledge of the pros and cons of surveillance mammography.

We hypothesize that our communication tool will lead to fewer women intending to receive surveillance mammography in the next year and women having more knowledge of the benefits and risks of surveillance mammography.

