- 8.4 Outcomes and Analyses for Aim 1.2. The outcomes of interest are shown in Table 2 below and have been adapted from [name] prior survey study testing a decision aid for screening mammography for older women.⁶⁶ We will focus on a primary outcome of intentions for mammography and will examine how various factors (race, health literacy, numeracy, anxiety, life expectancy) impact intentions. We use the sign rank and exact McNemar’s testing to compare the ‘pre’ vs. ‘post’ results for the continuous score for intention and proportion who indicate ‘yes’, respectively. To account for clustering by clinician, we will utilize random effects models if parametric assumptions hold, or alternatively using bootstrap resampling techniques to compute 95% confidence intervals for the change in intention. We anticipate a low number of missed surveys because of the CRC follow-up planned by phone, mail, or email if necessary. If a patient is missed for her ‘pre’ test survey, we will replace her to ensure enrollment of 45 with ‘pre’ and ‘post’ surveys. We will compare characteristics of those with missing surveys and missing questions to those with complete surveys to assess for any notable differences.

Table 2. Outcomes of Interest for Aim 1.2	
Outcome(s) of Interest	Outcome definitions, planned analyses

PROTOCOL TITLE:

Primary Outcomes: Patients: Frequency of change in intentions for mammography in the next year	15 point validated scale to assess ‘pre’ vs ‘post’ survey responses where scores 1-5 = yes to having mammography, 6-10 = unsure, 11-15 = no for mammography. We will use a continuous outcome of 1-15. ^{66,79}
Patients & Clinicians: Acceptability & Feasibility	Length, clarity; tabulate responses ⁸⁰ ; 75% report the tool is useful
Secondary Outcomes:	
Clinicians: satisfaction, time added/removed	Tabulate responses, prepare descriptive analyses
Patients: preferred decision-making role	‘Pre’ survey: Examine preferences for active, shared, passive decision-making ⁸¹
Patients: Decisional conflict	‘Pre’ vs. ‘Post’ survey: 16 item scale, Calculate total and sub-scale responses. Scores range 1-100, lower scores indicating higher quality decision-making ^{82,83}
Patients: Knowledge about mammography	Number of correct (10) knowledge questions on ‘pre’ vs. ‘post’ surveys. ^{66,84,85}

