Patients: intentions vs. actual decisions for mammography	‘Post’: Examine whether patient intentions for mammography agree with whether mammography is scheduled or not (using chart abstraction)
Patients & Clinicians: Agreement in intentions	‘Post’ for patients and providers: degree of agreement on scores 1-15
Patients & Clinicians: life expectancy wishes	‘post’ for patients and providers: tabulate responses for willingness to discuss

8.5 Primary Outcomes for Aim 1.2: We will focus on the primary outcomes of intentions for mammography and acceptability/ feasibility. We use the sign rank and exact McNemar’s testing to compare the ‘pre’ vs. ‘post’ results for the score for intention and proportion who indicate ‘yes’, respectively. To account for clustering by clinician, we will utilize random effects models if parametric assumptions hold, or alternatively using bootstrap resampling techniques to compute 95% confidence intervals for the change in intention. We anticipate a low number of missed surveys because of the CRC follow-up planned by phone if necessary. If a patient is missed for her ‘pre’ test survey, we will replace her to ensure enrollment of 45 with ‘pre’ and ‘post’ surveys. We will compare characteristics of those with missing surveys and missing questions to those with complete surveys to assess for any notable differences. For feasibility, we will declare the tool feasible if $\geq 75\%$ of patients and physicians report usefulness of the tool.

At the conclusion of this arm, we will have preliminary data on how the communication tool impacted care, its feasibility, and about multiple exploratory, secondary endpoints. If we have difficulties with recruitment of patients or clinicians for this project, we will contact additional clinicians and patients to reach our desired accrual goals. Given the high volume of breast cancer patients and clinicians in our system, we anticipate that accrual will occur with ease.

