****Baseline ('Pre') Patient Questionnaire****

Thank you for agreeing to participate in this study.

Study ID _____ (to be filled out by study team)

Date: _____

1. If your doctor or nurse asked you right now to make a choice about whether or not to get a mammogram, on a scale from 1-15 how certain are you about whether or not you would choose to get a mammogram in the next year? (1 means you are sure you would get a mammogram while 15 means you are sure you would not get a mammogram, if you are unsure please give a number between 1 to 15, 8 is the middle).

(If interview is being done over the phone because the in-person visit was missed, then ask patient: From 1-15, how likely are you to get a mammogram, 1 means you are certain I will get a mammogram and 15 means you are certain you will not get a mammogram. If you are not sure, please give a number between 1 and 15 that best describes how likely you are to get a mammogram)****

1	2	3	4	5	6	7	8	9	10	11	12	13	14	15
Will Get a Mammogram							Unsure				Will Not Get Mammogram			

As women age, the benefits of routine (when no symptoms are present) mammography may get smaller. As we try to learn from you, we would appreciate your honest answers to the questions below. These questions are about how you feel about whether or not to get a mammogram. Please say whether you Strongly Agree, Agree, are not sure, Disagree, or Strongly Disagree with the statements below.

2. I know which options are available to me for getting tested for breast cancer.

				
Strongly Agree	Agree	Not sure	Disagree	Strongly Disagree

3. I know the benefits of getting a mammogram.

				
Strongly Agree	Agree	Not sure	Disagree	Strongly Disagree

PROTOCOL TITLE:

4. I know the downsides or risks of getting a mammogram.

				
Strongly Agree	Agree	Not sure	Disagree	Strongly Disagree

5. I am clear about which benefits of getting a mammogram matter most to me.

				
Strongly Agree	Agree	Not sure	Disagree	Strongly Disagree

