****Post-visit Patient Questionnaire****

Study ID: _____

Date: _____

Thank you for agreeing to participate in this study. Now that you have had your visit with your provider, there are a few more questions that we would like you to answer.

If your health care provider asked you right now to make a choice about whether or not to get a mammogram, on a scale from 1-15 how certain are you about whether or not you would choose to get a mammogram in the next

PROTOCOL TITLE:

year? (1 means you are sure you would get a mammogram while 15 means you are sure you would not get a mammogram, if you are unsure please give a number between 1 to 15, 8 is the middle).

1	2	3	4	5	6	7	8	9	10	11	12	13	14	15
Will Get a Mammogram					Unsure					Will Not Get Mammogram				

(**If interview is being done over the phone because the in-person visit was missed, then ask patient: From 1-15, how likely are you to get a mammogram, 1 means you are certain I will get a mammogram and 15 means you are certain you will not get a mammogram. If you are not sure, please give a number between 1 and 15 that best describes how likely you are to get a mammogram)**

2. When do you plan to get your next mammogram?

- Never
- In the next year
- More than 1 year from now but less than 2 years from now
- More than 2 years from now
- Other: _____

The next set of questions are about how you feel about whether or not to get a mammogram and are the same questions we asked you before your visit today. Please say whether you Strongly Agree, Agree, Neither, Disagree, or Strongly Disagree with the statements below.

3. I know which options are available to me for getting tested for breast cancer.

- | | | | | |
|--------------------------|--------------------------|--------------------------|--------------------------|--------------------------|
|  |  |  |  |  |
| Strongly Agree | Agree | Not sure | Disagree | Strongly Disagree |

4. I know the benefits of getting a mammogram.

- | | | | | |
|--------------------------|--------------------------|--------------------------|--------------------------|--------------------------|
|  |  |  |  |  |
| Strongly Agree | Agree | Not sure | Disagree | Strongly Disagree |

5. I know the downsides or risks of getting a mammogram.

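### The phone script for the primary intention question drops the one-year horizon, so a woman planning a later mammogram can score differently by phone than in writing (minor)

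*Protocol*

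**What the plan says.** Section 1.0 of the protocol hypothesises that "our communication tool will lead to fewer women intending to receive surveillance mammography in the next year". Table 2 in Section 8.4 names the primary patient outcome as "Frequency of change in intentions for mammography in the next year", measured on a 15-point scale "where scores 1-5 = yes to having mammography, 6-10 = unsure, 11-15 = no for mammography". Sections 8.4 and 8.5 compare pre-visit with post-visit results by a signed-rank test on the score and an exact McNemar test on the proportion answering yes.

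In Appendix D, written item 1 of both patient questionnaires carries the horizon. The baseline form asks "how certain are you about whether or not you would choose to get a mammogram in the next year", and the post-visit form does the same. Each form then gives an alternative, introduced by "If interview is being done over the phone because the in-person visit was missed", which tells the caller to ask: "From 1-15, how likely are you to get a mammogram, 1 means you are certain I will get a mammogram". No horizon appears in that script.

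Phone completion is a planned fallback. Section 8.5 says "We anticipate a low number of missed surveys because of the CRC follow-up planned by phone if necessary", and the close of the baseline questionnaire tells the patient that the second survey may be completed by phone. A patient missed for her pre-visit survey is replaced: "test survey, we will replace her to ensure enrollment of 45".

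**The concern.** Two differently worded questions feed one primary score. Neither document has a rule for survey mode: the script is not aligned with the written item, recording of mode is not specified, and no analysis takes it into account.

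The wording matters most for a woman who means to skip the coming year and have a mammogram later. For the stated outcome she counts as not intending one, but the phone script invites her to say that she will have one. If her pre-visit answer was written and her post-visit answer was taken by phone, a genuine move away from mammography in the next year can be recorded as no change. The post-visit score is also used in two secondary outcomes in Table 2, agreement with scheduled mammography and agreement with the clinician, so the same misreading would carry into those.

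**Working it through.** The plan gives no power, effect size or standard deviation for Aim 1.2, so there is no figure to reproduce. The check sets the wordings side by side and then bounds the effect of one misread answer.

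**1. Wording (Appendix D, item 1, both forms)**

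| Feature | Written item | Phone script |
|---|---|---|
| Horizon | next year | none in the question, anchors or closing sentence |
| What is asked | certainty about the choice she would make if a clinician asked now | likelihood of getting a mammogram |
| Midpoint | 8 named as the middle | not named |
| Score | 1 = will, 15 = will not | same |

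In the post-visit form a page header interrupts the written sentence, but the horizon is there.

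**2. Who would answer differently.** Post-visit item 2 separates never, within the next year, one to two years away, and more than two years away.
- Stopping for good: near 15 on both versions.
- Going within the year: near 1 on both versions.
- Going later than one year: toward 15 in writing; toward 1 is a truthful answer by phone.

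Only the third group is clearly affected.

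**3. Which survey is by phone.**
- Written pre-visit, phone post-visit: the error is toward yes at post-visit, against the hypothesis.
- Phone pre-visit, written post-visit: the error is reversed and would exaggerate change. Section 5.3 allows phone contact to collect the pre-visit survey, so this can occur. It is less likely, because patients missed at pre-visit are replaced.
- Both by phone: the horizon is consistent, but it is not the one the outcome defines.

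**4. Size per misread woman.** Inputs: n = 45 (Section 4.1) and the scale bands in Table 2.
- Post-visit proportion answering yes: up to 1/45 = 2.2 percentage points.
- Mean change, ceiling (15 read as 1): (15 − 1)/45 = 14/45 = 0.31 points.
- Mean change, smallest move from the no band to the yes band (11 read as 5): (11 − 5)/45 = 6/45 = 0.13 points.

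The planned test of the score is the signed-rank test, which does not test the mean, so the mean shifts only indicate scale.

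**5. Exact McNemar test.** With discordant counts b and c, p = 2 × P(X ≥ max(b, c)), where X is binomial with b + c trials and probability 0.5. The counts below are illustrative; the documents give none.
- 6 versus 0: 2 × 1/64 = 0.031. If one of the six is read as yes at post-visit, 5 versus 0: 2 × 1/32 = 0.063.
- 8 versus 1: 2 × (9 + 1)/512 = 0.039. With one of the eight misread, 7 versus 1: 2 × (8 + 1)/256 = 0.070.

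When few pairs are discordant, one misread answer can move the result across 0.05. No phone share or deferral share is assumed, because the documents state neither.

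**The case against.** The best case against the point is that few women can be affected. A woman must be surveyed by phone, plan a mammogram only after more than a year, and hear the question as open-ended. Phone is a fallback: Appendix D makes REDCap the default with paper on request, Section 5.3 lists in person, mail or email for the post-visit survey, and Section 8.4 expects few missed surveys. Section 2.2 describes annual mammography as the recommendation in widely cited guidelines, so many women may take the question to mean the next annual test. Item 2 follows item 1 directly and can identify affected post-visit answers. The SAP names t-tests only for decisional conflict and lists no test of intention. The study is a pilot.

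Most of this stands, and it limits the point to a minor one. It does not remove it: the script replaces the defined question, phone use is planned, and no rule assigns item 2 a checking role. The items shown in the baseline form include no counterpart to item 2.

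Three stronger readings are tempting but unsupported.
- A reader might infer from post-visit item 44 that the study expects women to defer. That item records what the provider advised, and its deferral option leaves the decision open. It does not show a woman certain that she will have a later mammogram. The support is item 2.
- A reader might infer that the script favours the hypothesis. In the likelier mix of modes it works against it.
- A reader might want a number of misread women that would count as material. The documents set no threshold for a meaningful shift on the scale, so none can be given.

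**Conclusion.** The inconsistency is real and minor. Followed as written, the phone script can give a woman who plans a mammogram beyond one year a score that contradicts the outcome definition. In the likelier mix of modes this masks change. The per-woman effects above are bounds, and the total depends on how many such women are surveyed by phone, which is unknown and probably small.

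The conclusion assumes that the caller uses the script in place of the written item, as its instruction reads, and that some women with later plans take the question as open-ended. It bears on the intention comparison planned in protocol Sections 8.4 and 8.5. It does not show that phone answers in general are unusable, since women who will stop or will go within the year should mostly answer alike on both versions.

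**What to change.** In both questionnaires, replace the phone script with that form's written item read aloud word for word, including the one-year horizon and the same anchors. Record the mode of each survey in REDCap.

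If the present script has already been used and mode is known:
- report how many pre-visit and post-visit surveys used it;
- use item 2 to flag phone post-visit answers that refer to a mammogram more than a year away;
- keep the full analysis as the main one, and give the comparison restricted to pairs with both surveys in the written wording only as a sensitivity analysis. State that the restriction drops women who were harder to reach and who may differ from the rest.

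The cost is one scripted question in two forms that Section 9.3 still calls drafts, and one database field. The SAP is written in the past tense, so the script change may help only surveys still to come or the randomised study anticipated in Section 2.7. The count and the restricted comparison depend on mode having been recorded, which the documents do not say.

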****Post-visit Clinician Questionnaire****

Thank you for agreeing to participate in this study. We are going to ask you some questions relating to this particular visit with the patient. All of your answers will be kept confidential, will not be linked to your name for future use, and are for informational purposes only as we try to understand how helpful this tool was in your discussions with patients. Please answer openly and honestly and you can skip any question you prefer not to answer

Study ID _____

Date: _____

Intentions for mammography

1. What did you recommend in terms of mammograms for this patient?

- Continue having mammograms
- Get another mammogram but consider stopping after that
- It is the patient's choice
- To not get a mammogram now but reconsider later
- To stop getting mammograms
- Did not discuss mammograms
- Other: _____

2. Before the visit, what did you think you would recommend?

- Continue having mammograms
- Get another mammogram but consider stopping after that
- It is the patient's choice
- To not get a mammogram now but reconsider later
- To stop getting mammograms
- I did not think I would discuss mammograms
- Other: _____

3. During the visit today, did you discuss any of the following (circle each answer):

- | | | | |
|--|-----|----|----------|
| • Pros of mammograms? | Yes | No | Not sure |
| • Cons of mammograms? | Yes | No | Not sure |
| • The patients individual risk of in-breast, pre-cancer or invasive cancer events? | Yes | No | Not sure |
| • Family history? | Yes | No | Not sure |
| • Life expectancy? | Yes | No | Not sure |

PROTOCOL TITLE:

- Any other relevant discussion points you discussed?
-

3A. If yes to discussing life expectancy, how did this go? Check any that apply:

- Helpful to patient
- Helpful to me
- It was uncomfortable
- It was comfortable
- Made decision-making easier for mammogram
- Made decision-making harder for mammogram
- Neutral effect on decision-making
- Other _____

3B. If no to discussing life expectancy above, why not? Check any that apply

- It didn't come up
- I was uncomfortable talking about it
- Patient did not want to discuss it
- Patient was anxious
- Patient healthy so I didn't think it was important
- I didn't have time
- I didn't think it was important for this discussion

Questions about the Communication Sheet (with regard to its use during this visit with the patient)

4. The length of the communication sheet was

- | | | | | | |
|--------------------------|--------------------------|--------------------------|--------------------------|--------------------------|--------------------------|
|  |  |  |  |  |  |
| Much too Long | A little too long | Just right | A little too short | Much too short | I didn't use it |

5. The amount of information was

- | | | | | | |
|--------------------------|---------------------------|--------------------------|---------------------------|--------------------------|--------------------------|
|  |  |  |  |  |  |
| Much less than needed | A little less than needed | Just right | A little more than needed | Much more than needed | I didn't use it |

6. How clear was the information?

- | | | | | |
|--------------------------|--------------------------|--------------------------|--------------------------|--------------------------|
|  |  |  |  |  |
| Everything was clear | Most things were clear | Some things were clear | Many things were unclear | I didn't use it |

PROTOCOL TITLE:

7. I found the information

- | | | | | | |
|---|--|--------------------------|--|---|--------------------------|
|  |  |  |  |  |  |
| Clearly slanted
towards getting
a mammogram | A little slanted
towards getting
a mammogram | Completely
balanced | A little slanted
towards NOT
getting a mammogram | Clearly slanted
towards NOT
getting mammogram | I didn't
use it |

8. How helpful was the communication tool in making a decision about mammography?

- | | | | | | |
|--------------------------|--------------------------|--------------------------|--------------------------|--------------------------|--------------------------|
|  |  |  |  |  |  |
| Very helpful | Somewhat helpful | A little helpful | Not helpful | I didn't
use it | |

9. Would you recommend the use of this communication tool?

- | | | | |
|--------------------------|--------------------------|---------------------------|-----------------------------|
|  |  |  |  |
| Definitely
Recommend | Probably
Recommend | Probably not
Recommend | Definitely not
Recommend |

It would be helpful to learn how you prefer to use health educational materials such as the one you used today.

10. What is your preferred format for health education materials:

- A pamphlet like the one you used for this study
- The computer/internet
- No preference
- Other _____

11. How did using this tool affect the length of the visit with your patient today?

- Made visit a lot longer
- Made visit a little longer
- No effect on visit time
- Made visit a little shorter
- Made visit a lot shorter
- Not sure
- Other
- I didn't use it

12. Please let us know about any other thoughts you have about using the tool in practice. Please be as honest as possible.

Thank you so much for your help. You will receive a one-time \$40 at the end of this study for participating in these surveys.

PROTOCOL TITLE:

CITATIONS

****All questionnaires are adapted and revised from validated surveys used in the following publications :*

Decision Aid evaluation for screening by Schonberg M.A. et al JAMA Intern Med 2014; 174(416-424),

https://decisionaid.ohri.ca/docs/develop/User_Manuals/UM_ChoicePredisposition_Decision.pdf,

https://decisionaid.ohri.ca/docs/develop/Tools/DCS_English.pdf,

https://decisionaid.ohri.ca/docs/develop/Tools/Acceptability_osteoporosis.pdf)

Gotay CC and Pagano. Assessment of Survivor Concerns: A newly proposed brief questionnaire. Health Qual Life Outcomes 2007; 5: 15.

PROTOCOL TITLE:

**APPENDIX E: VERBAL CONSENT FOR THE PATIENT PHONE INTERVIEWS
AND FOCUS GROUPS**

